## **14.0 Risks and Benefits**

### **14.1 Risks of Harm:**

Identify all research-related risks of harm to which the subject will be exposed for each research procedure or intervention as a result of participation in this study. Consider the risks of breach of confidentiality, psychological, legal, social, and economic risks as well as physical risks. Do not describe risks from standard care procedures; only describe risks from procedures done for research purposes

Note: the risks associated with Ketorolac have been demonstrated to increase with dosage. The risks are listed and discussed below. Separately, due to the risks of the medication in general, the treating provider will be required to concur with the medication and dosage regimen in order for the patient to be enrolled in the study. This is outlined in the inclusion and exclusion criteria.

Non-steroidal anti-inflammatory drugs, such as ketorolac, have the following potential adverse effects: gastrointestinal hemorrhage, nausea, vomiting, dyspepsia, dizziness or lightheadedness, and somnolence. 1 Gastrointestinal hemorrhage is the most concerning because it also appears to be dose-dependent. The risk for gastrointestinal bleeding is highest for ketorolac out of all of the nonsteroidal anti-inflammatory drugs.4 Additionally, single doses of parenteral ketorolac have been demonstrated to interfere with platelet function by prolonging bleeding time, inhibiting platelet aggregation, and reducing platelet thromboxane production.5-7 Likewise, single doses of ketorolac at 15 mg and 30 mg intravenously and 60 mg intramuscularly have been shown to worsen hemorrhage in postoperative patients.8,9

There is a very low risk for harm with participation in this study as the medication is being administered as recommended by the package insert and as recommended by the Food and Drug Administration. Furthermore, patients who are at increased risk for these adverse events will not be enrolled in the study, based on questions asked using the inclusion and exclusion criteria during the consent process. Ketorolac has the following known adverse events with applicable percent of patients who experience these effects: headache (17%), gastrointestinal pain (13%), dyspepsia (12%), nausea (12%), edema (4%), hypertension, dizziness (7%), drowsiness (6%), diaphoresis, pruritus, skin rash, diarrhea (7%), constipation, flatulence, gastrointestinal fullness, gastrointestinal hemorrhage, gastrointestinal perforation, gastrointestinal ulcer, heartburn, stomatitis, vomiting, anemia, prolonged bleeding time, purpura, increased liver enzymes, pain at injection site (2%), tinnitus, and renal function abnormality.

Additionally, there is a risk that the study subjects receiving the 15 mg dose will have inadequate pain control.

There is also the risk of accidental disclosure of protected health information (PHI) or personally identifiable information (PII). However, name and MRN will only be listed on the Master Key. The remainder of the research data will only have the Study Subject Number.

There are specific risks to pregnant and breastfeeding women. There is an FDA boxed warning that ketorolac is contraindicated in labor and delivery due to the potential to inhibit uterine contractions and adverse effects on fetal circulation. Additionally, ketorolac has a pregnancy risk factor of C. In this category, risk to the mother and fetus cannot be ruled out.

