#### 12.6 Exclusion Criteria:

Order Number	Criteria
	
Patients weighing less than 50 kg (110 lbs)
 
Patients younger than 18 or older than 55 years
 
Pregnant or breast feeding

	History of: confirmed, unconfirmed, known, unknown, or suspected peptic ulcer disease, intestinal hemorrhage, renal insufficiency, hepatic insufficiency, cerebrovascular bleeding, hemorrhagic diathesis, incomplete hemostasis, dark stools, bright red blood per rectum, hemoptysis, easy bruising, or high risk of bleeding
	Unable to confidently convey or unknown medical history
	Allergy or hypersensitivity to nonsteroidal anti-inflammatory drugs or Aspirin
1	Systolic blood pressure <90 or >180 mmHg; pulse rate <50 or >150 beats/min
	Any over-the-counter or prescribed opioid and/or non-opioid analgesic medication (oral, per rectum, topical or parenteral) taken within 12 hours of ED presentation
	Advised by any medical provider to not receive non-steroidal anti-inflammatory drugs (NSAIDs) for any reason
	Pain duration greater than 30 days
	Refusal to remain in the WBAMC ED for up to 60 minutes after injection of ketorolac
	Patients currently taking anticoagulant medications
	Concurrent use of medications which are contraindicated with concomitant NSAID use. These drugs include aspirin, probenecid and pentoxyfylline

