## 14.2

### Measures to Minimize Risks of Harm (Precautions, safeguards):

For each research procedure or intervention, describe all measures to minimize and/or eliminate risk of harms to subjects and study personnel

The only intervention which will be provided for the conduct of this study is administration of intramuscular ketorolac at either a 15 mg or 60 mg dose. Ketorolac is a commonly used NSAID in the emergency department. There are a number of well-known potential side effects and contraindications to its use. We have outlined specific exclusion criteria to minimize harm and eliminate harm where possible.

During the pre-screening phase, patients with an ESI of 1-3 will be excluded. These patients are excluded because, by definition, their medical process may require multiple medical resources to evaluate and treat. Due to this complexity, there is higher likelihood that patients with an ESI of 1-3 will have underlying disease which may preclude the use of ketorolac. Additionally, during this prescreening process, patients with a systolic blood pressure less than 90 or greater than 180 mmHg and / or a pulse rate less than 50 or greater than 150 beats/min will be excluded. We have set these ranges as exclusion criteria as these values indicate that a more serious underlying pathologic process or multiple underlying pathologic processes are occurring, which could result in the patient requiring interventions beyond a single dose of ketorolac.

During the recruitment and consenting phases, patients will be thoroughly assessed for eligibility to participate in the study using our previously identified inclusion and exclusion criteria. This assessment has been developed with the subject's wellbeing and the greatest possible risk reduction in mind. These criteria were developed after careful analysis of known and potential adverse events and the contraindications, as outlined by the FDA. These criteria are discussed in depth below:

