1. We have outlined several specific criteria for women. First, all women will be required to provide a POC UHCG to ensure that they are not pregnant. Those that decline to or cannot provide a urine sample will be excluded. Additionally, women who are pregnant or breastfeeding will be excluded due to the pregnancy risk factor category C and because it is known that ketorolac crosses into breast milk. These criteria were developed to ensure that the risk of ketorolac administration to a pregnant or breast feeding subject is all but eliminated.
2. For all study subjects, there are exclusion criteria related to specific processes which are known to be exacerbated or caused by the use of ketorolac. These include known, unknown, or suspected allergy or hypersensitivity to NSAIDS, peptic ulcer disease, intestinal hemorrhage, renal or hepatic insufficiency, suspected or confirmed cerebrovascular bleeding, hemorrhagic diathesis, incomplete hemostasis, dark stools, bright red blood per rectum, hemoptysis, easy bruising, or high risk of bleeding. Additionally, potential subjects will be excluded if they have ever been advised by any medical provider to not receive non-steroidal anti-inflammatory drugs (NSAIDs) for any reason.
3. Due to the increased risk of adverse effects with higher doses of NSAIDS, patients will be excluded who have used over-the-counter or prescribed NSAID analgesic medication (oral, per

rectum, topical or parenteral) taken within 12 hours of ED presentation. This ensures that study subjects are not provided with NSAID doses above what is recommended.

4. Potential study subjects will be excluded who have any other medical concern identified either through patient history or through the review of systems. This criteria is set as it is the study's aim to evaluate the efficacy of intramuscular ketorolac for pain management, alone. It is not the intent of the investigators to withhold or prevent a complete evaluation and therapy for any medical condition identified during the study period.
5. Finally, potential subjects will be excluded who are unable to confidently convey or report unknown medical history. This prevents the administration of ketorolac in subjects with possible undiagnosed disease.

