#### Renal Effects

Long-term administration of NSAIDs has resulted in renal papillary necrosis and other renal injury. Renal toxicity has also been seen in patients in whom renal prostaglandins have a compensatory role in the maintenance of renal perfusion. In these patients, administration of a NSAID may cause a dose-dependent reduction in prostaglandin formation and, secondarily, in renal blood flow, which may precipitate overt renal decompensation. Patients at greatest risk of this reaction are those with impaired renal function, heart failure, liver dysfunction, those taking diuretics and ACE inhibitors, and the elderly. Discontinuation of

NSAID therapy is usually followed by recovery to the pretreatment state. Ketorolac tromethamine and its metabolites are eliminated primarily by the kidneys, which, in patients with reduced creatinine clearance, will result in diminished clearance of the drug (see CLINICAL PHARMACOLOGY). Therefore, ketorolac tromethamine should be used with caution in patients with impaired renal function (see DOSAGE AND ADMINISTRATION) and such patients should be followed closely. With the use of ketorolac tromethamine, there have been reports of acute renal failure, interstitial nephritis and nephrotic syndrome.

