	
concentrations, ketorolac tromethamine increased the incidence of chromosomal aberrations in Chinese hamster ovarian cells. Impairment of fertility did not occur in male or female rats at oral doses of 9 mg/kg (0.9 times the human AUC) and 16 mg/kg (1.6 times the human AUC) of ketorolac tromethamine, respectively.
 
Ketorolac tromethamine is contraindicated in patients with active peptic ulcer disease, in patients with recent gastrointestinal bleeding or perforation and in patients with a history of peptic ulcer disease or gastrointestinal bleeding.
 
Ketorolac tromethamine should not be given to patients who have experienced asthma, urticaria, or allergic-type reactions after taking aspirin or other NSAIDs. Severe, rarely fatal, anaphylactic-like reactions to NSAIDs have been reported in such patients (see WARNINGS – Anaphylactoid Reactions, and PRECAUTIONS – Preexisting Asthma).
 
Ketorolac tromethamine is contraindicated as prophylactic analgesic before any major surgery.
 
Ketorolac tromethamine is contraindicated for the treatment of peri-operative pain in the setting of coronary artery bypass graft (CABG) surgery (see WARNINGS).
 
Ketorolac tromethamine is contraindicated in patients with advanced renal impairment or in patients at risk for renal failure due to volume depletion (see WARNINGS for correction of volume depletion).
 
Ketorolac tromethamine is contraindicated in labor and delivery because, through its prostaglandin synthesis inhibitory effect, it may adversely affect fetal circulation and inhibit uterine musculature, thus increasing the risk of uterine hemorrhage.
 
The use of ketorolac tromethamine is contraindicated in nursing mothers because of the potential adverse effects of prostaglandin-inhibiting drugs on neonates.
 
Ketorolac tromethamine inhibits platelet function and is, therefore, contraindicated in patients with suspected or confirmed cerebrovascular bleeding, hemorrhagic diathesis, incomplete hemostasis and those at high risk of bleeding (see WARNINGS and PRECAUTIONS).
 
Ketorolac tromethamine is contraindicated in patients currently receiving aspirin or NSAIDs because of the cumulative risks of inducing serious NSAID-related adverse events.
 
The concomitant use of ketorolac tromethamine and probenecid is contraindicated.
 
The concomitant use of ketorolac tromethamine and pentoxifylline is contraindicated.
 
Ketorolac tromethamine injection is contraindicated for neuraxial (epidural or intrathecal) administration due to its alcohol content.

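### Section 12.6 omits one contraindication that the protocol itself lists (risk of renal failure from volume depletion) and the general medical exclusion stated in 14.2

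*Protocol*

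**What the plan says.** The contraindications entry in the drug details of section 18.2 includes: "Ketorolac tromethamine is contraindicated in patients with advanced renal impairment or in patients at risk for renal failure due to volume depletion". That sentence has two limbs, one for established kidney impairment and one for risk arising from fluid loss.

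The history item in 12.6 names "peptic ulcer disease, intestinal hemorrhage, renal insufficiency, hepatic insufficiency, cerebrovascular bleeding, hemorrhagic diathesis, incomplete hemostasis", followed by several signs of bleeding. It is qualified so that unconfirmed, unknown and suspected conditions count as well as confirmed ones. Section 12.6 also sets vital-sign limits: "Systolic blood pressure <90 or >180 mmHg; pulse rate <50 or >150 beats/min". Nothing in 12.5 or 12.6 mentions volume depletion, dehydration or hypovolemia.

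Sections 14.1 and 14.2 rest the protection of subjects on these lists. Section 14.1 states that patients "at increased risk for these adverse events will not be enrolled in the study, based on questions asked using the inclusion and exclusion criteria", and that "the medication is being administered as recommended by the package insert and as recommended by the Food and Drug Administration". Section 14.2 adds: "These criteria were developed after careful analysis of known and potential adverse events and the contraindications, as outlined by the FDA". When 14.2 goes through the criteria one by one, its item 4 reads: "Potential study subjects will be excluded who have any other medical concern identified either through patient history or through the review of systems". That item does not appear in 12.6.

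**The concern.** Section 12.6 is the list an investigator works from, and 14.1 and 14.2 treat it as carrying the label's contraindications into the trial. If one is missing, a patient to whom the drug should not be given can satisfy every listed criterion.

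The harm in question is renal. The Renal Effects text in 18.2 says that, in patients whose renal perfusion depends on prostaglandins, "a NSAID may cause a dose-dependent reduction in prostaglandin formation and, secondarily, in renal blood flow, which may precipitate overt renal decompensation". Section 14.1 includes abnormal renal function among the known adverse events. Section 10.1 (Medication Administration) ends data collection at 60 minutes and lists pain scores, adverse effects, blood pressure and heart rate, with no renal measurement. A renal event is therefore unlikely to appear in the trial data, and protection has to come before the injection.

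**Working it through.** The plan gives no figure to reproduce here, so the check is a comparison of text.

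**Step 1. Match each contraindication in 18.2 with 12.6.**

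| Contraindication in 18.2 | Treatment in 12.6 |
|---|---|
| Peptic ulcer disease, GI bleeding or perforation | Ulcer and intestinal bleeding items (perforation not named, but largely falls under them) |
| Allergic-type reaction to aspirin or NSAIDs | Allergy item |
| Advanced renal impairment | Renal insufficiency item |
| Risk of renal failure due to volume depletion | **No item** |
| Labor and delivery; nursing | Pregnancy and breast-feeding item |
| Cerebrovascular bleeding and other bleeding risk | Listed |
| Current aspirin or NSAIDs | 12-hour analgesic item; aspirin also named as a concurrent drug |
| Probenecid; pentoxifylline | Both named |
| Prophylaxis before major surgery; CABG pain; neuraxial route | Cannot arise in this trial |

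One applicable contraindication has no match. I give no proportion covered, because any count depends on how the label's sentences are split.

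**Step 2. Does another item in 12.6 reach the same patient?**
- The renal insufficiency item covers suspected or unknown insufficiency. It therefore reaches some volume-depleted patients, but being at risk of renal failure is not the same as having, or being suspected of having, renal insufficiency.
- The vital-sign limits are wide. Take systolic 95 mmHg and pulse 130 as an illustration: 95 is between 90 and 180, and 130 is between 50 and 150, so neither limit is breached. Section 14.2 explains these limits as markers of serious underlying disease, not as a check on volume status.

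**Step 3. Do the other eligibility statements name it?**
- Section 12.5 requires ESI 4 or 5 and the attending provider's concurrence; 12.1 restricts entry to patients who would routinely receive intramuscular ketorolac. None of these names the condition.
- Section 14.2, item 2, restates the excluded conditions and again gives renal and hepatic insufficiency without volume depletion.
- Section 14.2, item 4, is broad enough to include it, but is absent from 12.6.

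**Step 4. Compare with what is claimed.** Section 14.2 traces the criteria to the FDA contraindications, and Step 1 shows one that did not carry over. In 14.1, the adverse events referred to could be read as those of the preceding paragraph, which does not name renal events, or as the list later in the same paragraph, which does. The mismatch with 14.2 does not depend on that reading.

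**The case against.** The strongest reply is that the trial already excludes this patient. Item 4 of 14.2 presents itself as a criterion and covers any further medical concern found on history or review of systems. The renal item reaches suspected and unknown disease. ESI 4 or 5 selects low-acuity patients. The attending takes a separate history, must agree to the dose and writes the prescription. The Renal Effects text, where it names the patients at greatest risk, does not mention volume depletion. Most of this stands, and it is why the expected effect is small. What remains is that no control names the condition, and the broadest one is not in the list used for screening.

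Some stronger readings are tempting, but the documents do not support them:
- *That nobody will ask about fluid loss.* Section 10.1 says the review of systems is contained in the application. Its content is not in the supplied text, so it may well ask. The finding is only that the contraindication is not a listed criterion.
- *That attending refusals would fall more heavily on the 60 mg arm.* The contraindication as written is not limited by dose, so an attending applying it would refuse 15 mg as well. Exclusion after a refused dose is a separate design question and lends this point no weight.
- *That the fourfold dose difference (60/15 = 4) or the loss allowance (122 - 110 = 12 subjects) measures the gap.* Neither says how many volume-depleted patients would enter.
- *That SSRIs, corticosteroids, diuretics and ACE inhibitors should also be exclusions.* In 18.2 these are cautions or risk factors, which can properly be left to the attending's judgement.

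**Conclusion.** The point holds in a narrow form and is worth considering. Section 12.6 lacks one contraindication that 18.2 lists and one exclusion that 14.2 states, so the assurances in 14.1 and 14.2 go slightly further than the list supports. No reason is given for either omission, which suggests oversight.

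The expected effect is small and confined to safety; the treatment estimate, alpha, power and sample size are untouched. This judgement assumes that volume depletion is uncommon among ESI 4 or 5 musculoskeletal patients aged 18 to 55, and that the general controls work as described. The documents give no frequency with which to test the first assumption, so no count of exposed subjects is offered.

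**What to change.** 1. Add to 12.6: *Known or suspected volume depletion (for example recent vomiting, diarrhea, heat illness or poor fluid intake)*.
2. Copy the general exclusion of 14.2, item 4, into 12.6.
3. Add both to the exclusion checklist on the Ketorolac Research Form, since 10.1 says that form documents the exclusion criteria.
4. Ask about fluid loss with the other eligibility questions during the consent process (13.4, 14.1), before signature and before the attending is told the assigned dose. The recruitment synopsis in 13.1 is a scripted overview given before consent and is not the place for a health question. If the review of systems already contains the question, it need only be asked at this point.

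The cost is two exclusion lines, one checklist change, one question, a minor amendment and possibly a few more screen failures. Randomization and analysis stay as they are. The SAP's wording suggests that analysis may have begun; if recruitment is over, the correction serves the larger multicenter study anticipated in 9.6 and 14.4.

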## 14.2

### Measures to Minimize Risks of Harm (Precautions, safeguards):

For each research procedure or intervention, describe all measures to minimize and/or eliminate risk of harms to subjects and study personnel

The only intervention which will be provided for the conduct of this study is administration of intramuscular ketorolac at either a 15 mg or 60 mg dose. Ketorolac is a commonly used NSAID in the emergency department. There are a number of well-known potential side effects and contraindications to its use. We have outlined specific exclusion criteria to minimize harm and eliminate harm where possible.

During the pre-screening phase, patients with an ESI of 1-3 will be excluded. These patients are excluded because, by definition, their medical process may require multiple medical resources to evaluate and treat. Due to this complexity, there is higher likelihood that patients with an ESI of 1-3 will have underlying disease which may preclude the use of ketorolac. Additionally, during this prescreening process, patients with a systolic blood pressure less than 90 or greater than 180 mmHg and / or a pulse rate less than 50 or greater than 150 beats/min will be excluded. We have set these ranges as exclusion criteria as these values indicate that a more serious underlying pathologic process or multiple underlying pathologic processes are occurring, which could result in the patient requiring interventions beyond a single dose of ketorolac.

During the recruitment and consenting phases, patients will be thoroughly assessed for eligibility to participate in the study using our previously identified inclusion and exclusion criteria. This assessment has been developed with the subject's wellbeing and the greatest possible risk reduction in mind. These criteria were developed after careful analysis of known and potential adverse events and the contraindications, as outlined by the FDA. These criteria are discussed in depth below:

1. We have outlined several specific criteria for women. First, all women will be required to provide a POC UHCG to ensure that they are not pregnant. Those that decline to or cannot provide a urine sample will be excluded. Additionally, women who are pregnant or breastfeeding will be excluded due to the pregnancy risk factor category C and because it is known that ketorolac crosses into breast milk. These criteria were developed to ensure that the risk of ketorolac administration to a pregnant or breast feeding subject is all but eliminated.
2. For all study subjects, there are exclusion criteria related to specific processes which are known to be exacerbated or caused by the use of ketorolac. These include known, unknown, or suspected allergy or hypersensitivity to NSAIDS, peptic ulcer disease, intestinal hemorrhage, renal or hepatic insufficiency, suspected or confirmed cerebrovascular bleeding, hemorrhagic diathesis, incomplete hemostasis, dark stools, bright red blood per rectum, hemoptysis, easy bruising, or high risk of bleeding. Additionally, potential subjects will be excluded if they have ever been advised by any medical provider to not receive non-steroidal anti-inflammatory drugs (NSAIDs) for any reason.
3. Due to the increased risk of adverse effects with higher doses of NSAIDS, patients will be excluded who have used over-the-counter or prescribed NSAID analgesic medication (oral, per

rectum, topical or parenteral) taken within 12 hours of ED presentation. This ensures that study subjects are not provided with NSAID doses above what is recommended.

4. Potential study subjects will be excluded who have any other medical concern identified either through patient history or through the review of systems. This criteria is set as it is the study's aim to evaluate the efficacy of intramuscular ketorolac for pain management, alone. It is not the intent of the investigators to withhold or prevent a complete evaluation and therapy for any medical condition identified during the study period.
5. Finally, potential subjects will be excluded who are unable to confidently convey or report unknown medical history. This prevents the administration of ketorolac in subjects with possible undiagnosed disease.

Separate from the stated exclusion criteria, the risks of administration of the intramuscular ketorolac have been considered in the study's design. As such, all current policies and procedures for the administration of intramuscular medications, as outlined by the Joint Commission, WBAMC, and the WBAMC ED, will be followed.

The data management and methodology for this study mitigates confidentiality risks by de-identifying all subject data documented for the purposes of this study. Subjects will be assigned a Subject Study Number for the data collection and subsequent reporting and building of the final study report.

